##### **D2. Aim 2:**

Group differences in the SEFAS scores will be analyzed using a t-test or Mann-Whitney test at the 14 day, 3, and 6 month time points...

D2. Aim 3:

The times the patient enters and is discharged from the PACU will be recorded. Discharge from the PACU is based on several criteria, one of which is adequate pain control. Hence duration of PACU stay is relevant to pain experienced by the subject but there may be non-pain related reasons for prolonging the PACU stay. Verbal pain scores on a scale of 0 (least painful) to 10 (worst pain imaginable) are recorded periodically by the nursing staff and entered into the chart; the timing of these entries cannot be expected to be completely uniform and patients with higher pain may be queried more often. Pain scores will therefore be summarized by an area-under-the curve analysis, using a score of 3 as a reference value. A simple average of all pain ratings captured in the PACU will also be examined. Both sets of values will be compared between experimental and control groups using the t-test or Mann-Whitney test, as appropriate.

Time and amount of opioid medications will be captured from the PACU record. Different opioid drugs will be converted into analgesic equivalents using the values presented at <http://www.globalrph.com/narcotic.htm>. Total equivalent opioid use will be compared between experimental and control groups using the t-test or Mann-Whitney test.

D4. Aim 4:

Demographic and clinical data will be compared between the groups to determine if values differ significantly despite randomization (table \*\*\* below). A preliminary analysis of possible confounding clinical variables that may influence the development of chronic pain will be conducted. Linear regression analysis will be used to examine the contributions of these 3 variables and the treatment group (experimental or control) to the SEFAS score at 12 months. It is expected that this small pilot study will lack the power to fully analyze confounders, but the analysis may be used to guide future, larger studies.

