## **B. Specific Aims and Hypotheses**

Aim 1: Test the hypothesis that SEFAS scores at the one year time point are higher (better outcome) in subjects who received a ropivacaine pump compared to patients who received standard care. This is the primary outcome measure).

Aim 2: Test the hypothesis that SEFAS scores at earlier time points (14 day, 3 month, 6 month) are higher in subjects who received a ropivacaine pump compared to patients who received standard care.

Aim 3: Test the hypothesis that pain scores and total opioid use in the PACU are lower in subjects receiving the ropivacaine pump.

Aim 4: Conduct a preliminary examination of possible roles of confounding clinical and demographic variables, focusing on: severity of ankle fracture; sex; and body mass index (BMI).

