#### **D. Statistical Analysis Plan**

For categorical variables, counts and percentages will be presented. As a check on randomization, groups will be compared using the Fisher's exact test. For continuous variables, mean, median, standard deviation (SD) and inter-quartile range (IQR) will be presented. Groups will be compared using the t-test, except that non-parametric methods will be used for variables distributed non-symmetrically.

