##### **D1. Aim 1:**

Each SEFAS response has 5 ordinal response choices scored 0 through 4. With 12 items and with the lowest score (0) representing the most severe disability, the total score ranges from 0 to 48. If a subject omits one or more questions, the total score will be re-normalized to 48. Group differences in the SEFAS scores at the 12 month time point will be analyzed using the t-test or Mann-Whitney test, as appropriate.

Patients who are withdrawn from the study due to failure of the initial nerve block will be considered as screening failures; no follow-up data or questionnaire scores will be obtained. The same approach will be taken for patients who decide to withdraw from the study, or are withdrawn by the attending surgeon or anesthesiologist, after randomization but before the single shot nerve block procedure.

Patients lost to follow-up after the end of the 5 day nerve block will be analyzed with a per-protocol analysis. We consider that, since the follow-up begins after the end of the treatment and consists only of completing questionnaires, there is unlikely to be a bias towards the experimental or control group having drop-outs.

Patients who have to (or choose to) remove the pump before the entire 5 day treatment period will be analyzed both an intent-to-treat analysis and a per-protocol analysis. The duration of pump use will be noted.

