## I. Mock tables to be produced

Table 1: Descriptive table of demographics of experimental and control groups prior to intervention.

Description	Control (N = ***) 	Experimental (N = ***) 	p value
Age at ankle surgery (years)			
Weight at time of surgery			
Height at time of surgery			
BMI at time of surgery			
Race			
Ethnicity			
Ankle fracture: number of malleoli affected			
Grade of injury (defined as closed injury, or open injury with Gustilo Anderson classification grade 1, grade 2, grade 3a, grade 3b, grade 3cr) 			
Time in surgery			
Estimated blood lost in surgery			
Number of plates implanted			
Total length of plates implanted			
Total number of screw holes in implanted hardware			

Mean, SD, median, interquartile range for continuous variables, number and % per group for categorical variables.

 Converted to ordinal scale 1 – 6

Table 2 Pain outcomes

Description	Control (N = ***)	Experimental (N = ***)	p value
Opioid medication use in PACU: analgesic equivalents			
Time in PACU			
PACU discharge status (home, rehab facility, hospital) 			
PACU Pain score AUC			

Average Pain score in PACU			
SEFAS score (2 week)			
Pain medication use analgesic equivalents (2 week)			
SEFAS score (3 month)			
Pain medication use analgesic equivalents (3 month)			
SEFAS score (6 month)			
Pain medication use analgesic equivalents (6 month)			
SEFAS score (12 month)			
Pain medication use analgesic equivalents (12 month)			
Number (%) with any chronic pain diagnosis at 12 months			

 Converted to ordinal scale 1 – 3

Table 3 Other outcomes

Description	Control (N = ***)	Experimental (N = ***)	p value
Number (%) requiring re-operation			
Number (%) : Indication for re-operation (infection, non-union, hardware failure, hardware removal, other)			
Wound healing status at first FU (dehiscence, cellulitis , deep infection, healing well, other) 			
Wound healing status at second FU (dehiscence, cellulitis , deep infection, healing well, other) 			
Weight bearing current status at first FU [full, assisted (cane, walker, boot), non (crutch)] 			
Weight bearing current status at second FU [full, assisted			

(cane, walker, boot), non (crutch)] 			
---	--	--	--

 Converted to ordinal scale

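### The primary 12-month SEFAS comparison is unadjusted, although a covariate model is already planned and randomisation is stratified by site; balance is left to Table 1 p-values that cannot do the job

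*SAP*

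**What the plan says.** **Primary analysis.** SAP D1 (Aim 1) states: "Group differences in the SEFAS scores at the 12 month time point will be analyzed using the t-test or Mann-Whitney test, as appropriate". No covariate and no site term is mentioned. Protocol section 12 names only the Mann-Whitney test.

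**Covariate model.** SAP B (Aim 4) picks out fracture severity, sex and BMI. Under D4: "Linear regression analysis will be used to examine the contributions of these 3 variables and the treatment group (experimental or control"), with SEFAS at 12 months as the outcome. The SAP calls this preliminary and concedes that power to analyse confounders will be low.

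**Stratification.** Protocol section 7 gives the West Chester and Uptown locations separate randomisation schedules because their populations are thought to differ. Site is in neither analysis, nor in the SAP section E variable list.

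**Balance.** SAP D says of categorical variables: "As a check on randomization, groups will be compared using the Fisher's exact test". It gives the t-test or a non-parametric method for continuous ones. D4 adds: "Demographic and clinical data will be compared between the groups to determine if values differ significantly despite randomization". Mock Table 1 in SAP I, titled "Descriptive table of demographics of experimental and control groups prior to intervention", has 13 rows and a p-value column. Sex is not a row, although SAP E collects it as gender. No action is tied to any of these p-values.

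**The concern.** The trial collects variables that may be prognostic and plans a model containing both them and the treatment arm, yet keeps that model out of the primary analysis. With about 20 patients per arm, a chance imbalance in a prognostic factor can shift the primary estimate by an amount that matters beside the 9-point target. An adjusted analysis fixed in advance would remove much of that shift. If the covariates are prognostic enough, it would also narrow the interval.

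The tool chosen to deal with imbalance is significance testing. Under sound randomisation, every significant baseline row is a chance finding. At this sample size, imbalances large enough to matter go unflagged. Five rows (time in surgery, blood loss, number of plates, total plate length, screw holes) are fixed during an operation that follows randomisation in an open-label trial, so they cannot check the randomisation.

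**Working it through.** **Inputs.** From Protocol section 12: 20 per group, a 9-point difference, power 0.8, alpha 0.05. From SAP I: 13 Table 1 rows. From Protocol section 7: randomisation before surgery. Not in the documents, so assumed: a two-sided test, a 0.05 threshold for the balance tests, and the share of SEFAS variance that covariates explain (R²).

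**1. The plan's own figure.** The SD is taken from a cited study and not stated, so the sample size cannot be confirmed directly. Solving for the SD that gives exactly 0.80 power:
- normal approximation: 10.16
- t-test, 38 df: 9.90 (9/9.90 = 0.909 SD)
- Mann-Whitney at 0.955 efficiency: about 9.66

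Twenty per group is therefore coherent for an SD of about 9.7 to 10.2. I use 9.9.

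**2. False alarms in Table 1.**
- 13 independent rows: 1 − 0.95^13 = 0.487, with 13 × 0.05 = 0.65 expected. This is an upper figure, because weight, height and BMI are related, so are the three hardware rows, and Fisher's test is conservative.
- Simulation with an assumed correlation structure: about 0.35, with 0.54 expected.
- The eight rows fixed before randomisation (age, weight, height, BMI, race, ethnicity, malleoli, injury grade), if independent: 1 − 0.95^8 = 0.337.

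**3. Missed imbalances.** For an observed gap of g SD at 20 per arm, t = g × √(20/2). With g = 0.5, t = 0.5 × 3.162 = 1.58 on 38 df, so p is about 0.12 and the row is not flagged. For any one covariate, a chance gap this large in either direction occurs in about 11% of trials (normal approximation). Its effect on the arm difference is r × g × SD, where r is the covariate's assumed correlation with SEFAS. For r = 0.2 the shift is 0.2 × 0.5 × 9.9 = 1.0 point. For r = 0.4 it is 2.0 points.

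**4. Power of an adjusted analysis.** Noncentral t with k covariates, df = 38 − k, residual variance 9.9² × (1 − R²), inflated by 37/(37 − k) for chance imbalance. Unadjusted t-test: 0.80.

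| R² (assumed) | k = 1 | k = 2 | k = 3 |
|---|---|---|---|
| 0 | 0.79 | 0.78 | 0.76 |
| 0.10 | 0.83 | 0.82 | 0.81 |
| 0.20 | 0.87 | 0.86 | 0.85 |
| 0.30 | 0.91 | 0.90 | 0.89 |

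Setting the formula equal to 0.80 gives a break-even R² of about 0.03, 0.06 and 0.085 for one, two and three covariates. In simulation (5,000 trials per R²), three covariates gave 0.76, 0.80, 0.85 and 0.89 at the four R² values. Mann-Whitney gave about 0.77 to 0.78, so against that test the break-even for three covariates is only about 0.03.

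**The case against.** The strongest reply is that nothing here is invalid. A randomised comparison needs no adjustment, and its standard error already allows for chance imbalance. An adjusted estimate will be available from Aim 4, so the dispute is over which estimate is called primary. A pilot may reasonably prefer the simpler one, especially for a bounded 0 to 48 score. All of that stands. A reader might infer that the unadjusted result is biased; the documents do not support that.

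A reader might also infer that the plan certainly gives up power. It does not follow. The SAP says only that these variables may influence chronic pain, and no document gives their prognostic strength. The first SEFAS is at 14 days, so there is no pre-treatment score to act as a strong covariate. Three useless covariates would lower power by about 4 points.

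Third, a significant Table 1 row triggers no decision. Comparing the arms is also not pointless here: Protocol section 7 lets assignments depart from the schedule when no ropivacaine is available. This justifies describing balance. It does not justify p-values, which are weak at this size. The intra-operative rows do precede the infusion, so the table's title can be defended, but they still follow randomisation.

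What the reply leaves unanswered is that site was thought important enough to stratify on and then dropped from every analysis, and that the Aim 4 severity measure is not defined. SAP E lists both number of malleoli and injury grade, so the choice could be made with unblinded data in hand.

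**Conclusion.** The concern holds as a matter of efficiency, robustness to chance imbalance, and reporting. It is not an error that invalidates the primary comparison. The benefit of adjustment rests on an assumed R². At the stated design with three covariates, power ranges from 0.76 (R² = 0) to 0.89 (R² = 0.30) against 0.80 unadjusted, so the covariate list should be short. The 49% false-alarm figure is a ceiling; about 35% is the more realistic size, under an assumed correlation structure and a 0.05 threshold. The Table 1 changes alone would be reporting edits. The substantive step is to fix the adjusted primary model in advance.

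**What to change.** 1. In SAP D1, make the primary estimate the treatment coefficient from a linear model of 12-month SEFAS on arm, site and one or two pre-randomisation prognostic variables already collected, for example one named fracture-severity measure. Fix the list now, whatever balance is later observed.
2. Keep the unadjusted t-test or Mann-Whitney test as a sensitivity analysis.
3. Add site to the SAP section E data set, and align Protocol section 12, which names Mann-Whitney.
4. Report Table 1 descriptively. Delete its p-value column and the statements in SAP D and D4 that the arms will be tested for baseline differences. Add sex, and move the five intra-operative rows to a separate descriptive table.

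No new data collection is involved; the cost is SAP wording and a matching protocol change. The statistical cost is about 1 point of power for each covariate that explains nothing, so site and any other covariate should be kept to those expected to matter.

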**E. Variables in the analysis data set with Definitions**

Description
Patient unique ID
Age at ankle surgery
Date of ankle surgery
Weight and height at time of surgery
Date of enrollment
Gender
Race
Ethnicity
Randomized to control or experimental group?
Ankle fracture: number of malleoli affected
Grade of injury (defined as :closed injury, or open injury with Gustilo Anderson classification grade 1, grade 2, grade 3a, grade 3b, grade 3cr)
Opioid medication use in PACU: time, agent, dose, and route for each administration
Times entered and discharged from PACU
PACU discharge status (home, rehab facility, hospital, AMA)
Verbal pain scores in PACU (0 – 10 scale) and times at which recorded
Surgical Hardware: number of plates implanted, length and number of screw holes of each.
Estimated blood loss during surgery
Pain medication prescription at discharge (drug, dose)
Start time of surgery
End time of surgery
SEFAS score (2 week, 3, 6, 12 month post surgery)
Subject-reported analgesic use (2 week, 3, 6, 12 month post surgery)
Dates of post-surgical follow-ups (FU)
Weight bearing recommendation at each FU (non, partial, full, other)
Weight bearing current status at each FU [full, assisted (cane, walker, boot), non (crutch)]
Pain status at each FU (none, mild, severe)
Pain medication prescriptions at each FU (drug, dose)
Wound healing status at each FU (dehiscence, cellulitis , deep infection, healing well, other)
Range of motion at each FU
Re-operation required?
Date of re-operation

Indication for re-operation (infection, non-union, hardware failure, hardware removal, other)
Chronic pain conditions diagnosed at one year FU.

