PACU and recorded in the electronic record, until the patient is discharged from the PACU. Chart review of the follow-up orthopedic appointments will be used to identify possible development of chronic pain conditions or unforeseen complications of 5 day pump use.

8. Specimen collection: not applicable.

9. Potential Benefits:

Possible benefits to the subject during the time the pump is in use include better postoperative pain control, improved sleep, and reduced need for opioids with their concomitant side effects and risk of abuse [26]. Preclinical data (see above) and some clinical data in other conditions provide some support for the hypothesis being tested that the nerve block will reduce the risk of chronic pain [27]. If this pilot study is successful and can be extended to a full study large enough to fully test this hypothesis, the research may contribute generalizable knowledge to improve practices in combat medicine and trauma medicine.

10. Potential Risks, Discomforts, and inconveniences:

Level of risk: Greater than minimal risk

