### A. Introduction:

This is a pilot study to determine whether prolonged continuous peripheral nerve blockade, given for a duration longer than is customary in clinical practice, can reduce the incidence of chronic pain after ankle fracture. Patients undergoing surgery for open reduction and internal fixation of ankle fractures will be randomized to standard care (single shot peripheral nerve block prior to surgery) or experimental (the same single shot nerve block, followed by continuous popliteal nerve block with ropivacaine starting just after surgery). The primary outcome will be scores on a

validated ankle/foot pain questionnaire that includes questions on function (Self-Administered Foot and Ankle Questionnaire, SEFAS). Subjects will be followed for one year, with SEFAS scores administered at 14 days, and 3, 6, and 12 months following the ankle surgery. Secondary outcomes are postoperative opioid use in the Post-Anesthesia Care Unit (PACU), and pain ratings in the PACU. Data will also be obtained regarding the feasibility of doing a larger study. Preliminary analysis of possible confounding variables will be conducted, but as this is a pilot study it is anticipated that there may not be enough subjects to yield significant findings about patient subgroups.

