## **C. Study Design**

This is an investigator-initiated, single-center, prospective, non-blinded, randomized pilot study. We are authorized to enroll up to 60 patients to allow for 40 evaluable subjects.

Adults undergoing surgery for open reduction and internal fixation for traumatic ankle fracture will be invited to participate in the study comparing the 2 forms of nerve block. All patients are currently given the option of popliteal nerve block (single injection of ropivacaine given just prior to surgery), which helps provide pain relief in the immediate postoperative period; the surgery itself is done under general anesthesia. Participants who have agreed to have the single shot procedure will be randomized into the control group (standard-of-care single popliteal injection of local anesthetic just prior to surgery) or experimental group (standard-of-care single injection plus 5 day ambulatory popliteal nerve block).

The treatment will be open label due to the impracticality of blinding the physician or patient to the presence of local anesthetic in the 5 – day pump and the ethical barriers to subjecting patients to implantation of a catheter and empty or saline pump with no benefit to them. Per standard of

care, patients in both the experimental and control groups will also have other oral pain medications prescribed for use as needed.

Standard-of care procedures will be used for placement of the single shot popliteal nerve block. In the experimental group, in addition to the standard single shot nerve block, subjects will receive a catheter to deliver continuous 5 day popliteal sciatic nerve block using a disposable ambulatory pain pump. The catheter will be inserted just prior to surgery. A portable pump will be attached to the catheter at the time the block is placed, and continuous block with 0.2% ropivacaine will begin immediately after surgery when the patient arrives in the PACU.

Additional data routinely obtained for clinical purposes will also be collected including demographic variables, analgesic use in the PACU, and details of the ankle fracture and surgery.

The standard follow-up appointments with the orthopedic surgeons following ankle surgeries are at 10 - 14 days, 5 – 6 weeks, and 3 – 4 months. Chart review of these follow-up appointments will be used to extract additional clinical variables.

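### The 12-month chronic pain diagnosis compared between arms has no one-year visit behind it, so the row can show only what happens to be in the chart

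*SAP*

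**What the plan says.** SAP section A states the question as whether prolonged block "can reduce the incidence of chronic pain after ankle fracture". Section E lists the variable "Chronic pain conditions diagnosed at one year FU", and Table 2 in section I reports it as "Number (%) with any chronic pain diagnosis at 12 months", with a column per arm and a p value.

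On where such a diagnosis would come from:

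- **Visits.** SAP section C says the standard orthopedic appointments "are at 10 - 14 days, 5 – 6 weeks, and 3 – 4 months". Protocol section 6 gives the same schedule.
- **Source of clinical variables.** SAP section C: "Chart review of these follow-up appointments will be used to extract additional clinical variables".
- **Source for chronic pain.** Protocol section 7: "Chart review of the follow-up orthopedic appointments will be used to identify possible development of chronic pain conditions".
- **Contact at 12 months.** Protocol section 6 describes SEFAS and medication use collected by internet, post or telephone.

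Neither document gives diagnostic criteria, an assessor, a time window, a denominator or a rule for patients with no chart entry near one year.

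**The concern.** A proportion is interpretable only if each subject had a comparable chance of being found to be a case. Here no trial procedure makes a diagnosis at one year. A patient enters the numerator only after seeking care that reached the chart and receiving a diagnosis there. The row would then mix chronic pain with care-seeking and recording habits, under a label that reads as 12-month incidence.

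Recording may also be unequal between arms. Protocol section 6 describes a regular chart review, at least monthly, for the experimental group only. Protocol section 13 says pump receipt is noted in the Epic chart for treating physicians to see, so any later diagnosis is made with knowledge of the arm. The pilot is meant to inform a larger study, and a misread incidence could be carried into its design.

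**Working it through.** **1. Can the planned sources produce the variable?** The documents give no figure for chronic pain incidence to reproduce; the only sample-size statement (protocol section 12) concerns SEFAS. The check is therefore to match each source in SAP section G against the variable.

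| Source | What it holds at 12 months |
|---|---|
| EPIC chart review | Only unscheduled care, since the last scheduled visit is at 3–4 months |
| REDCap SEFAS export | A score, with no cut-off defining chronic pain |
| Opioid conversion table | Nothing about diagnosis |

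Only the chart can supply a diagnosis, and no planned visit puts one there at one year. Of the other pain measures, SEFAS and 12-month analgesic use are tabulated as quantities, and pain status at each follow-up appears in no mock table. The diagnosis row is thus the only planned output that is an incidence.

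**2. What would under-recording do, if absence of a record were read as no chronic pain?** This is an illustration.

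- From the documents: 20 per group (protocol section 12), and a background figure of 20% to 50% (protocol section 5), which would be 20 × 0.20 = 4 to 20 × 0.50 = 10 controls. The 20–50% is a literature figure, not a 12-month clinic-diagnosis rate.
- Assumed: treatment halves the true rate, and a share *s* of true cases is charted, equal in both arms.
- Observed difference = *s* × (control rate − experimental rate).
- Power is the summed binomial probability of all tables with two-sided Fisher p ≤ 0.05. Fisher's test is the one the SAP names for categorical variables.

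| True rates | Difference, *s* = 1 | Power | Difference, *s* = 0.5 | Power |
|---|---|---|---|---|
| 20% v 10% | 10.0 points | 7% | 5.0 points | 2% |
| 35% v 17.5% | 17.5 points | 16% | 8.8 points | 6% |
| 50% v 25% | 25.0 points | 27% | 12.5 points | 10% |

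The absolute difference shrinks in proportion to *s*. The risk ratio does not change: 35/17.5 = 17.5/8.75 = 2. Even with every case recorded, power is at most 27% in these scenarios, so the p value would tell the reader little.

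**3. What if patients with no record were excluded instead?** The error can then run the other way. Suppose the true rate is 35%, and 50% of cases but only 25% of non-cases have a chart contact near 12 months (both assumed). Among those with a contact the rate is (0.35 × 0.50) / (0.35 × 0.50 + 0.65 × 0.25) = 0.175 / 0.3375 = 52%.

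**4. What if recording differs by arm?** With no treatment effect, a true rate of 35% in both arms and assumed recording of 40% in one arm and 60% in the other, the row shows 0.35 × 0.40 = 14% against 0.35 × 0.60 = 21%. The documents do not say which arm would be recorded more fully.

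**The case against.** The strongest reply is that the SAP turns its question into something measurable through SEFAS, not through this row. SAP section B names SEFAS at one year as the primary outcome, the instrument centres on pain and its functional impact, and it is sought from every subject at 12 months. The diagnosis row belongs to none of Aims 1–4. This stands, and it limits how much the point matters.

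A second reply is that later chart information is not ruled out. SAP section G lists EPIC review without a time limit, protocol section 6 says consent covers records of chronic pain diagnoses, and the follow-up variables in SAP section E are not expressly confined to the three visits. The limit of 3 months after pump use sits in the safety-monitoring paragraph of protocol section 6. A diagnosis charted at 3–4 months could also be found at a 12-month review. All of this is fair, but access to the chart recovers only what someone recorded. It does not create an assessment at one year.

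A reader might infer that patients who do not return after 3–4 months are counted as free of chronic pain. The documents do not say so. No coding rule is written, and such patients could equally be missing or excluded. The lost-to-follow-up sentence in SAP section D1 mentions only a per-protocol analysis and does not settle the matter. It is a risk, because a count over an arm-level N filled from the chart leaves unrecorded patients out of the numerator, but it is not a stated rule.

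On differential recording, the monthly review is a safety measure, and reading a chart does not itself generate a diagnosis. The two protocol statements show that unequal recording is possible, not that it will occur.

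**Conclusion.** The point holds in a limited form. The plan would report, as a 12-month incidence with a p value, a quantity that depends on unscheduled care and unblinded charting, without criteria, window, denominator or missing-data rule. That goes beyond missing detail, because completing the table as laid out would mislabel what was measured.

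The size and direction of the bias cannot be derived from the documents. Every recording fraction and every treatment effect used above is an assumption; the figures show only that the result moves with the recording share and with the unstated coding choice.

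Two stronger conclusions are tempting and unsupported. One is that the trial has no other measure bearing on chronic pain: 12-month SEFAS and analgesic use are collected from subjects directly. The other is that the main inference is compromised: the row is not a named primary or secondary outcome, and the primary SEFAS comparison does not use it.

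**What to change.** - **Relabel and demote the row.** Call it *chronic pain diagnosis recorded in chart by 12 months*, present it descriptively and remove its p value.
- **Equalise ascertainment.** State one chart-review window and procedure for this variable and apply it to both arms.
- **If a 12-month proportion is wanted,** derive it from the 12-month SEFAS pain items and reported analgesic use. The documents contain no cut-off, so fix one before any arm-level data are seen. Use 12-month respondents as the denominator and show non-respondents as missing in each arm.

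The cost is SAP wording, a changed table row and, for the optional part, one derived variable from data already planned. The downside of that part is a self-report definition that overlaps with the primary outcome, and it remains open to non-response, so the number missing should be shown beside the proportion.
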